Have there been any serious adverse events (serious and/or unanticipated problems involving risks to subjects or others at this site which occured in the past year)?

No

Have all study staff with a significant role in the design or implementation of the human subject components of this study received required training in human research subject protections?

Yes

Is the study covered by a certificate of confidentiality?

No

Overall Progress

Approved sample size

40

Total number of participants enrolled to date

ς

Number of participants who have completed the study to date

6

Have there been any significant deviations from the anticipated study recruitment, retention or completion estimates?

Yes

Describe actions taken or planned to address these problems.

Recruitment was less than expected, so data is being analyzed for the small sample actually collected.

Comments / additional information

Sample Demographics

Specify population

SAD

Total number of participants enrolled from this population to date

7

Specify population #2

OCD

Total number of participants enrolled from this population to date

Gender, Racial and Ethnic Breakdown

Gender: Female: 5 Male: 3

Race: Other: N=2 Caucasian: N=2

African American: N= 3

Asian: N=1

Ethnicity:
Hispanic: 1
Non-Hispanic: 7

Summary of Current Year's Enrollment and Drop-out

Number of participants who signed consent in the past year

2

Did the investigator withdraw participants from the study?

No

Did participants decide to discontinue study involvement?

No

Procedures

To create the protocol summary form, first indicate if this research will include any of the following procedures

- ✓ Psychiatric Assessment
- ✓ Medication Trial
- ✓ Use of Placebo or Sham Treatment
- ✓ Off-label Use of Drug or Device

Population

Indicate which of the following populations will be included in this research

- ✓ Adults
- ✓ Adults over 50

Research Support/Funding

Will an existing internal account be used to support the project?

Yes

Describe internal account

The study will use an RFMH account

Is the project externally funded or is external funding planned?

No

Study Location

Indicate if the research is/will be conducted at any of the following

✓ NYSPI

This protocol describes research conducted by the PI at other facilities/locations

No

Lay Summary of Proposed Research

Protocol Summary Form 7293 [name]

Lay Summary of Proposed Research

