Proven obsessive-compulsive disorder (OCD) and social anxiety disorder (SAD) treatments include medications called serotonin reuptake inhibitors (SRIs) and cognitive-behavioral therapy (CBT). However, up to half of OCD and SAD patients do not achieve wellness from these treatments. Thus, new treatments are needed.

This study will examine the efficacy of disrupting fear reconsolidation with propranolol hydrochloride (HCI), a method recently found effective in adults with spider fears but not yet tested in OCD or SAD, in 2 pilot randomized controlled trials (one in OCD, one in SAD).

A total of 20 adults with OCD, and 20 adults with SAD, between the ages of 18 and 60 years will participate in the study.

Background, Significance and Rationale

Background, Significance and Rationale

The two first-line treatments for OCD and SAD are a class of medications called serotonin re-uptake inhibitors (SRIs) and disorder-specific cognitive behavioral therapy. However, up to half of patients with OCD or SAD do not achieve wellness from these treatments.

Recent research suggests that pharmacologically modulating the process of fear memory reconsolidation may be a promising therapeutic avenue in the treatment of fear-related disorders such as OCD and SAD. For example, in a spider phobic sample, Soeter and Kindt (2016) administered 40mg of propranolol HCI after reactivating spider fear (by presenting a tarantula for 2 minutes) to disrupt reconsolidation of the fear memory. Participants who received propanolol HCI had reduced fear at two-week follow up compared to participants who received placebo. One year later, the benefits were maintained.

We propose two small pilot randomized placebo-controlled trial to test whether disrupting fear reconsolidation using propranolol HCI in adult OCD and SAD patients leads to a significant reduction in OCD and SAD symptoms and a significant improvement in a standardized behavioral avoidance test (BAT). We will study the subgroup of SAD patients with performance only fears related to public speaking, because these circumscribed fears may be most responsive to the treatment tested here. The intent is to collect pilot data on the feasibility, acceptability, and preliminary efficacy of this approach in OCD and SAD patients to support grant application for a future randomized controlled trial with a longer follow-up.

Specific Aims and Hypotheses

Specific Aims and Hypotheses

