The goal of these pilot studies is to investigate whether disrupting fear reconsolidation with propranolol HCI in adult OCD and SAD patients is feasible and leads to a reduction in OCD and SAD symptoms and an improvement in a Behavioral Avoidance Task (BAT).

Description of Subject Population

Sample #1

Specify subject population

Adult individuals with OCD

Number of completers required to accomplish study aims

20

Projected number of subjects who will be enrolled to obtain required number of completers

25

Age range of subject population

18-60

Sample #2

Specify subject population

Adult individuals with public speaking fears and SAD, performance only type

Number of completers required to accomplish study aims

20

Projected number of subjects who will be enrolled to obtain required number of completers

25

Age range of subject population

18-60

Gender, Racial and Ethnic Breakdown

Based on the community from which we will be drawing patients and proportions to those encountered during previous clinical trials at this site, we expect the sample to be approximately 5% Hispanic and 95% Non-Hispanic; racially there will be 89% White, 9% Black, 2% Asian. Based upon the prevalence of OCD, it is expected that the sample will be approximately 1:1 =male:female.

Description of subject population

Females and male adults with a diagnosis of OCD or SAD (performance only type) and clinically significant symptoms of OCD or fear of public speaking.

All ethno-racial groups will be recruited.

Recruitment Procedures

Describe settings where recruitment will occur

Recruitment will draw from the broadest possible population with respect to gender and ethnic origin. Participants will be enrolled through the Anxiety Disorders Clinic, located on the third floor of the New York State Psychiatric Institute.

How and by whom will subjects be approached and/or recruited?

OCD and SAD patients will be recruited by physician or mental health practitioner referrals, or patient or

family referrals following advertisement of our work.

How will the study be advertised/publicized?

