Select the names of persons designated to obtain consent/assent 2
[name], MD
[name], MD
[name], MD
Type in the name(s) not found in the above list

Study Procedures

Describe the procedures required for this study

VISIT 1. Screening/evaluation for eligibility (conducted under IRB #6112R - Anxiety Disorders Clinic and Hispanic Treatment Program Screening and evaluation Process) and study consent followed by BAT.

Patients deemed eligible following phone screening will undergo with their written consent: 1) a clinical interview by a senior clinician (M.D. or Ph.D.) that will include a MINI for DSM-5; 2) a physical examination (i.e., history, physical, EKG test, and urine pregnancy test [for females]) by an MD; ; and 3a) for OCD patients a Y-BOCS for OCD severity; 3b) for SAD patients LSAS and PRCS for SAD and public speaking fear severity; 4) and HDRS to assess depression severity. ; and 5) a personalized Behavioral Avoidance Task (BAT) by a trained rater. Those who meet entry criteria will provide written informed consent for this study and then complete a personalized Behavioral Avoidance Task (BAT) by a trained rater. The BAT for OCD patients will assess degree of fear (using a subjective 0-100 scale) and overt approach behavior while being exposed to an OCD trigger (e.g. a toilet in patients with contamination fears). For SAD patients it will assess fear during a brief speech task. Following this procedure, participants will be dismissed for the day and they will be re-contacted to schedule visit 2 once their EKG and blood results come back and it is confirmed that they are eligible to complete the study.

Those who meet entry criteria will provide written informed consent for this study and then enter the baseline assessment and intervention.

VISIT 2. Consent, Baseline assessment (independent evaluator) and intervention

Consent and Baseline Assessment: After participants have signed consent, An independent evaluator will assess global psychopathology (CGI); depressive symptoms (HDRS); and anxiety symptoms (DASS). OCD patients will also be assessed for OCD symptoms (YBOCS), and

Protocol Summary Form 7293 [name]

SAD patients will also be assessed for SAD (LSAS) and fear of public speaking (PRCS). Then participants within each disorder will be randomized to one of two groups. Randomized assignments will be generated using a random number generator in SPSS using a block design.

Intervention:

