Participants are free to withdraw from the study at any time for any reason. Participants who discontinue will be given referrals, exactly as is done for study completers. Study doctors are to discontinue patients from the study if patients:

- Are determined to be ineligible to proceed after review of EKG and lab results
- Request early discontinuation or withdrawal of consent.
- Experience a serious or intolerable adverse event that prevents the patient from continuing.
- In the Investigator's opinion, are experiencing a clinically significant deterioration. For example, if a patient became suicidal or their symptoms of depression increased such that the depressive symptoms were much or very much worse relative to baseline and the HDRS-17 is no longer <20 (1 week follow-up evaluation), they would be discontinued from the study.
- Commit a protocol violation, including lack of compliance.
- Are "lost to follow-up."
- Encounter other conditions (such as administrative issues or pregnancy).

If a patient discontinues from the study at any time at their own request or at the study doctor's discretion, the reason(s) for discontinuation are to be recorded by the study. Patients withdrawing from the study for reasons related to the study medication (usually adverse events) will be followed until the event(s) have resolved or no further action is required.

Blood and other Biological Samples

Please create or insert a table describing the proposed collection of blood or other biological specimens NA

Assessment Instruments

Create a table or give a brief description of the instruments that will be used for assessment

- MINI- International Neuropsychiatric Interview (MINI, 1 hour). The MINI is a semi-structured clinician rated instrument that assesses the major adult Axis I disorders in DSM-5.
- Yale-Brown Obsessive Compulsive Scale (Y-BOCS, 45 minutes) This is a semi-structured clinician rated instrument used to measure obsessions and compulsions separately over five separate dimensions (time consumed, distress, interference, degree of resistance, control). This is the gold-standard measure or OCD symptoms.

- Liebowitz Social Anxiety Scale (LSAS, 10 minutes). Clinician rated instrument assessing fear and avoidance of 24 situations.
- Personal Report of Confidence as a Speaker (PCRS, short form, 10 minutes) 30-item self-rating about public speaking fears.

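### Does a sample size of 40 conflict with the projection of 50 enrolled to obtain 40 completers?

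*Combined protocol and SAP*

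**What the plan says.** Three places in the combined protocol and SAP give a size for the study.

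- **Overall Progress** (progress report): the entry for "Approved sample size" is 40. The next lines are "Total number of participants enrolled to date", whose value is not legible in the text available, and the number who have completed, which is 6.
- **Lay Summary of Proposed Research**: "A total of 20 adults with OCD, and 20 adults with SAD" are to take part, again 40 in all.
- **Description of Subject Population**, Samples #1 and #2: the entry for "Number of completers required to accomplish study aims" is 20 in each disorder, and the entry for "Projected number of subjects who will be enrolled to obtain required number of completers" is 25 in each.

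The order of events bears on what each count could mean. Study Procedures, Visit 1, has participants consent, do the behavioural avoidance task and go home; "they will be re-contacted to schedule visit 2 once their EKG and blood results come back". Allocation comes at Visit 2: "Then participants within each disorder will be randomized to one of two groups". Criteria for Early Discontinuation includes people who "Are determined to be ineligible to proceed after review of EKG and lab results".

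**The concern.** The figure 40 appears twice without a label, and 25 + 25 = 50 appears once with one. A reader who takes the approved 40 as a cap on enrolment will conclude that the study was never authorised to enrol the number it says it needs, and that its own attrition allowance leaves it short of the completers it calls required.

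The label could matter because consent, randomisation and completion fall at different times, and some loss may come before randomisation. Feasibility is a stated goal in Specific Aims and Hypotheses, and Background, Significance and Rationale says the pilot data are meant to support a grant application. Recruitment and completion rates with an uncertain denominator would weaken that use.

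**Working it through.** **Reproducing the stated figures.**

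- Lay Summary: 20 + 20 = 40, equal to the approved size.
- Required completers: 20 + 20 = 40, also equal to the approved size.
- Projected enrolment: 25 + 25 = 50, which differs from 40 by 10 people (10/50 = 20% of projected enrolment).

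So 40 reproduces exactly as the number of completers and does not reproduce as projected enrolment. None of the sums is wrong.

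**Implied completion.** 20/25 = 0.80, an implied loss of 20%. The document states no dropout rate, so inflating 20 by this rate to recover 25 (20/0.80 = 25) is circular. It shows that 25 is a possible attrition allowance. It does not show that 80% was a forecast.

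**The three readings of 40.**

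| Reading | Expected completers per disorder | Agrees with 20 completers from 25 enrolled? |
|---|---|---|
| Completers | 20 | Yes, no shortfall |
| Randomised | 20 × 20/(25 − k), where k of the 5 losses come before randomisation: 16.0 at k = 0, 20.0 at k = 5 | Depends on k, which the document does not give |
| Enrolment ceiling | 20 × 0.80 = 16 (32 overall) | No, 4 short per disorder |

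The figure of 16 needs two assumptions that the document does not make: that 40 is a ceiling on enrolment, and that 20/25 is an expected completion rate. With assumed dropout of 10%, 20%, 25% or 30%, 20 enrolled would give 18, 16, 15 or 14 completers.

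**How firm the 25 is.** If each participant completes independently with probability 0.80, the chance of at least 20 completers from 25 is about 62%, and from 20 it is 0.8^20, about 1.2%. Even the projected 25 would not make 20 completers certain, so it is better read as a planning margin.

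**What the least favourable reading would cost.** Completers per arm would fall from 10 to 8 in each disorder. The document states no alpha, power, effect size or SD, so the next step assumes a two-sided 5% test, 80% power and the normal approximation. The detectable standardised difference is (1.96 + 0.84) × √(2/n):

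- n = 10: 1.25 SD
- n = 8: 1.40 SD

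Both are very large effects. The plan claims power for neither, so no stated property of the design is lost.

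**Actual recruitment.** The progress report records 7 participants with social anxiety disorder, a gender breakdown that sums to 5 + 3 = 8, and 6 completers. All are far below 40, so neither 40 nor 50 limited anything.

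**The case for a change.** The strongest case for a change is that the harmless reading is never stated. The progress report has separate lines for enrolled and for completed, and gives the approved size neither label. The Lay Summary speaks of people taking part, which more naturally covers everyone who enters than only those who finish. Description of Subject Population shows that the authors write completers when they mean completers. A pilot with feasibility as a goal should have a clear denominator, and adding a label costs nothing.

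Most of that is fair as a description of the text: the 40 is unlabelled, and the wording in those two places leans slightly towards enrolment. The step from there to a shortfall does not stand. The approved size heads a block that reports both enrolment and completion, so its position settles little. It is nowhere called a limit.

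The argument from pre-randomisation loss is also less secure than it looks. Visit 1 and the discontinuation criteria support consent before the EKG and laboratory review. But Visit 2 is also headed as a consent visit, and Consent Procedures places consent after eligibility has been determined under the separate screening protocol. On that version, people who fail the review might never count as enrolled here, and their loss would not be part of the step from 25 to 20.

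A final report that gives numbers consented, randomised and completed per disorder would supply the feasibility denominator whichever meaning 40 had. That is ordinary reporting practice and needs no amendment.

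**Conclusion.** The concern does not call for a change. The document gives an unlabelled 40 in a progress field and a lay summary. The section that sets the sample labels 20 completers and 25 enrolled per disorder and so provides for attrition. Read as completers, the 40 agrees everywhere. Read as enrolled, it differs from the projection by 10 people. Nothing in the document decides between the two, but no figure is shown to be wrong, and the expected 16 per disorder holds only if 40 is an enrolment ceiling and 80% an expected completion rate.

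A label would be harmless but would gain nothing now. No analysis, test, power claim or stopping rule uses 40 or 50. The progress report already discloses a significant departure from the recruitment, retention or completion estimates, explains that recruitment was low, and says that the small sample is being analysed. This conclusion rests on the absence of any power-based justification that depends on the enrolment count, and on recruitment having ended well short of both figures.

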Depending on rates of response, IRB-approved advertisements and flyers will be posted both online and in the local community (e.g., in and around the CUMC campus). Online advertisements may be posted on websites dedicated to obsessive compulsive disorder or psychiatry research [e.g., our own clinic website (www.columbia-ocd.org), www.ocfoundation.org, Columbia clinical trials website] and on such community websites as Craigslist.org, Myspace.com, Facebook.com, Friendster.com, Livedeal.com, Citynews.com, Adwords.google.com, ResearchMatch.org, Topix.net and Columbia RecruitMe. For web-based forums or discussion groups that are open only to patient members, permission to recruit will be obtained from group leaders prior to posting.

Do you have ads/recruitment material requiring review at this time?

Yes

Does this study involve a clinical trial?

Yes

Please provide the NCT Registration Number

NCT02790710; NCT02790736

Concurrent Research Studies

Will subjects in this study participate in or be recruited from other studies?

Yes

Describe concurrent research involvement

All participants in the current study will be screened under "IRB #6112R - Anxiety Disorders Clinic and Hispanic Treatment Program Screening and evaluation Process."

Eligible subjects who have finished other studies in the Anxiety Disorders Clinic will be offered participation. These protocols will include:

IRB#6628. Attaining and maintaining wellness in OCD.

IRB#7000. Control and Reward Circuits in OCD.

IRB#7127. Toward Precision Medicine for OCD.

IRB#7059 Pilot study of personalized-computerized inhibitory control training for OCD.

IRB# 6837 Internet Based Treatment for OCD (iCBT.)

Participants will be allowed to participate in other studies at our center at the same time if these studies do not involve treatment (e.g. IRB#7127 Toward Precision Medicine for OCD or IRB#711. Stress Reactivity in Patients with Anxiety).

After finishing the study, participants will be allowed to participate in other treatment and non-treatment studies at our center if they meet the eligibility criteria for those studies.

Participants will be re-screened if there is a delay of more than 4 weeks between screening and participation.

Inclusion/Exclusion Criteria

Name the subject group/sub sample Adult OCD participants

Create or insert table to describe the inclusion criteria and methods to ascertain them

CRITERION	METHOD OF ASCERTAINMENT

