3) Moderately/severely depressed patients with HDRS-17 (17-item Hamilton Depression Rating Scale) >20 or judged clinically to be at risk of suicide.	Clinical Interview/MINI and HDRS-17		
4) SAD patients with SAD not of the performance only type.	MINI, Liebowitz Social Anxiety Scale score >60		
5) Female patients who are either pregnant or nursing.	Clinical interview, medical exam, and Urine pregnancy test		
6) Patients planning to commence CBT during the period of the study or currently in CBT treatment.	Clinical interview		
7) Current substance use disorders (meeting criteria within the past 3 months, with the	Clinical interview		

exception of nicotine).	
8) History of any significant medical condition that	Clinical interview and medical history, and
might increase the risk of participation due to the	medical examination including blood pressure,
effects of propranolol (e.g., seizure disorder,	heart rate, and EKG.
respiratory disorders [e.g., bronchial asthma],	
cardiovascular disease [e.g., congestive heart	
failure, heart arrhythmias, sinus bradycardia and	
greater than first degree block], low blood	
pressure [< 90/60], diabetes, liver or kidney	
disorders) or current use of medications that may	
negatively interact with a one time dose of 40 mg	
of propranolol (e.g., ACE inhibitors;	
catecholamine depleting drugs, such as reserpine;	
calcium channel blockers; digitalis glycosides;	
haloperidol; chlorpromazine; aluminum hydroxide	
gel; phenytoin; phenobarbitone; rifampin;	
antipyrine; lidocaine; cimetidine; theophylline)	

Waiver of Consent/Authorization

Indicate if you are requesting any of the following consent waivers
Waiver of consent for use of records that include protected health information (a HIPAA waiver of Authorization)

No

Waiver or alteration of consent

No

Waiver of documentation of consent

No

Waiver of parental consent

No

Consent Procedures

Is eligibility screening for this study conducted under a different IRB protocol?

Yes

Indicate NYSPI IRB#

6112R

Describe Study Consent Procedures

After determining eligibility under 6112R the subjects will go over the consent for this study and have

questions answered by the consenter. If the subject agrees the consent form will be signed and the study begun.

Indicate which of the following are employed as a part of screening or main study consent procedures

✓ Consent Form

Persons designated to discuss and document consent

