OCD participants will receive a short exposure (2') to an OCD phobic stimulus trigger (e.g. a toilet). SAD participants will be asked to prepare and give a short (2 minute) speech before an audience of several staff members. These exposures will be conducted by either a psychologist or psychiatrist on the study team.

After that, half of the OCD participants and half of the SAD participants will receive a single oral dose of propranolol HCI 40 mg. The other half of participants (within each diagnostic group) will receive a placebo. Following the administration of the propanolol or placebo participants will be asked to wait in the Anxiety Disorders Clinic for 90'. The participant's blood pressure, heart rate, and possible side effects will be assessed (using a side-effects checklist) at three time points: before the short exposure, after the administration of the propranolol/placebo, and after the 90' waiting period. Participants will be told that the intervention they have received may help them overcome their fears during the following 2 weeks. They will be asked to keep a daily record of their avoidance/approach behaviors (for OCD patients, using the avoidance item from the self-report YBOCS). OCD participants will be also asked to assess daily their OC symptoms using two visual separate visual analogue scales (VAS), one for obsessions and one for compulsions. SAD participants will assess their public speaking fears daily using a VAS for anxiety and a VAS for avoidance.

Follow-up (independent evaluator)

After 1 week, participants will be contacted on the phone by the independent evaluator to assess depressive, and anxiety symptoms during the past week (using the HDRS-17, DASS, and CGI). OCD patients will also complete the YBOCS, and SAD patients will complete the LSAS and PRCS.

VISIT 3. Final assessment (independent evaluator)

After 14 days, participants will be assessed in our clinic by the independent evaluator with the same instruments (i.e., YBOCS, LSAS, PRCS, HDRS-17, DASS, and CGI) used in the baseline. In addition, the BAT conducted at screening will be repeated to measure any change in avoidance. The daily records of OC avoidance/approach behaviors as well as their VAS will then be collected.

You can upload charts or diagrams if any

Criteria for Early Discontinuation

Criteria for Early Discontinuation

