A number of drug interactions with propranolol HCI have been described. These include CYP450 substrates, inducers, and inhibitors; CYP2D6 substrates/inhibitors; hepatic enzyme inducers; etc (see http://www.pdr.net/drug-summary/Propranolol-Hydrochloride-Tablets-propranolol-hydrochloride-1400 for a complete list). Participants taking any of these drugs will be not eligible for the current study.

Propranolol HCI has been also used as a treatment for anxiety disorders (n>200, only including randomized controlled trials) using daily doses of up to 320 mg/day for up to 6 weeks (Steenen et al., 2016). No side effects were reported in a double-blind placebo controlled study using a single dose of propranolol HCI (80 or 120 mg) in dental phobia (n=23) (Liu et al., 1991).

In this protocol participants are being given just one 40 mg dose of propranolol and therefore no significant side effects are expected.

Propranolol has been used to disrupt fear reconsolidation in several human experimental studies involving hundreds of healthy participants (e.g. Kindt et al., 2009: Soeter & Kindt, 2010, 2011a, 2011b, 2012a, 2012b) and more than 70 patients with anxiety disorders (Brunet et al., 2008, 2011; Soeter & Kindt, 2015) (see Giustino et al., 2016 for a review) and no significant risks/side effects have been reported. Human research has shown that the declarative components of memory remain intact following propranolol-induced

reconsolidation blockade and that disruption of reconsolidation by noradrenergic receptor antagonism is memory specific and does not eliminate associated or non-reactivated memories (Otis et al., 2015)

Risks associated with delay in treatment initiation:

[name] and her clinical research team will be in contact with the OCD and SAD patients every week throughout this two week protocol. If a patient suddenly meets any exclusion criteria (e.g., active suicidal ideation) or no longer met the inclusion criterion of being "able to tolerate a treatment-free period," the patient would be removed from the study and referred for treatment. Patients may refuse to participate at any point and seek outside treatment.

Risks associated with assessment:

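### The urine pregnancy test that verifies an exclusion is scheduled only at Visit 1, with no repeat before the dose at the later Visit 2 (low-priority safety improvement)

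*Combined protocol and SAP*

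**What the plan says.** **The exclusion.** The OCD and SAD criteria both require women to be non-pregnant and also list as an exclusion "Female patients who are either pregnant or nursing". The stated means of ascertainment are interview, medical examination and a urine pregnancy test, with the test placed in screening.

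**When the test is done.** Study Procedures, VISIT 1, includes "a physical examination (i.e., history, physical, EKG test, and urine pregnancy test [for females]) by an MD". After the behavioural avoidance task, "participants will be dismissed for the day and they will be re-contacted to schedule visit 2 once their EKG and blood results come back", so dosing falls on a later day.

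**The dosing visit.** The heading is "VISIT 2. Consent, Baseline assessment (independent evaluator) and intervention". The steps listed are consent, rating scales, randomisation, a 2-minute exposure and then the study drug: half of each sample "will receive a single oral dose of propranolol" (40 mg) and the other half receive placebo. Blood pressure, heart rate and a side-effects checklist are recorded three times, starting before the exposure. No pregnancy test appears.

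**Time limit.** Concurrent Research Studies states: "Participants will be re-screened if there is a delay of more than 4 weeks between screening and participation". *Participation* is not defined.

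**Other safeguards.** Criteria for Early Discontinuation includes "Encounter other conditions (such as administrative issues or pregnancy". The text on risks of delayed treatment provides for removal: "If a patient suddenly meets any exclusion criteria". Eligibility is also to be confirmed before Visit 2, when the EKG and blood results are back.

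**The concern.** Pregnancy status can change between two visits on different days, and an early pregnancy can be missed by one test. The protocol chose not to rely on self-report for this exclusion, yet the test result it relies on belongs to a different day from the dose. A woman with a negative Visit 1 test whose pregnancy was missed, or began afterwards, and is still unrecognised at Visit 2 could be randomised and dosed with every written step followed. Discontinuation for pregnancy cannot undo a single dose already taken.

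What is at stake is participant safety and the enforcement of the protocol's own criterion. No estimate, test or sample size depends on it.

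**Working it through.** The plan states no figure for the age of the test at dosing, so the check sets the schedule entries side by side.

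**1. Where a pregnancy test is named**

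| Place in the protocol | Pregnancy test named? |
|---|---|
| Inclusion and exclusion tables, both samples | Yes, at screening |
| VISIT 1 | Yes |
| VISIT 2, consent and baseline | No |
| VISIT 2, intervention | No |
| 1-week phone follow-up and VISIT 3 | No |

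The entry for blood and other biological samples is marked not applicable, which is consistent with no further urine sample under this protocol.

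**2. Oldest test compatible with the text**

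Test age at dosing = date of Visit 2 − date of Visit 1.

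- *Reading A:* participation means the Visit 2 intervention. Re-screening is triggered only after more than 4 weeks, so the oldest test allowed is 4 × 7 = 28 days.
- *Reading B:* participation starts with consent at Visit 1. Consent Procedures says the study begins once the form is signed, and Study Procedures places consent at both visits. The 4-week rule then does not govern the gap between Visit 1 and Visit 2, and no limit is stated.

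Waiting for EKG and blood results sets the earliest date for Visit 2. It does not set a latest date.

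**3. What each safeguard detects**

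| Safeguard | Acts on | Would it find an unrecognised pregnancy? |
|---|---|---|
| Eligibility confirmed before Visit 2 | EKG and blood results | No repeat pregnancy test named |
| Only those meeting entry criteria go on to baseline and intervention | Information already held | No test named |
| Removal if an exclusion is met | A known change | No test named |
| Discontinuation for pregnancy | A known pregnancy | No test named |

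**4. How many doses a change could still reach**

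The enrolment total in Overall Progress is not legible in the supplied text. Sample Demographics lists 5 women and 3 men, so 5 + 3 = 8. Six participants have completed, so about 8 − 6 = 2 at most had not, and they may already have been dosed. This takes completers from a gender tally and is approximate. The same form says that the small sample collected is being analysed.

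**5. Effect of a repeat test**

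Test age at dosing becomes 0 days, compared with up to about 28 days under Reading A and no stated limit under Reading B. Sample size and analysis do not change.

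**The case against.** The strongest reply is that no rule in the protocol is broken. It says that pregnancy is ascertained at screening, and the schedule does that. Nothing requires a test on the dosing day, and the EKG is not repeated then either. This stands: the point is an improvement to the design and does not show an inconsistency. Against it, the protocol does not treat screening values as sufficient throughout. Blood pressure and heart rate are taken again before the exposure and dose, and the depression rating is repeated at Visit 2.

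A second reply is that a repeat test, or an instruction about pregnancy, may exist in screening protocol 6112R or in the consent forms. Neither was available, so this cannot be ruled out.

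A third is that no harm is shown. Exposure is one 40 mg dose or placebo, the documents give no fetal-risk figure, and pregnancy is not among the contraindications they list for propranolol. This also stands and limits the priority.

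A reader might infer three stronger things that the documents do not support:

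- *That 4 weeks is a firm ceiling on the age of the test.* It depends on an undefined word, as Reading B shows.
- *That a known pregnancy could pass through to dosing.* The eligibility, discontinuation and removal provisions cover that case.
- *That 20 to 25 women are exposed to the gap.* A 1:1 sex ratio gives 40 × 0.5 = 20 at the approved sample and 50 × 0.5 = 25 at the projected enrolment (25 + 25 = 50). That sample was not reached. The protocol bases the ratio on OCD prevalence only, and not every woman aged 18 to 60 could become pregnant.

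**Conclusion.** The point holds as a low-priority safety improvement. In the supplied text, the test that verifies the pregnancy exclusion is scheduled only at Visit 1, no test precedes the dose at Visit 2, and no window between the visits is fixed. The test may be up to about 4 weeks old at dosing on the assumption that participation means the Visit 2 intervention; otherwise no limit is stated. The gap is narrow: it concerns only a pregnancy missed by, or arising after, a negative Visit 1 test and still unrecognised at Visit 2. The documents give no probability for this.

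The conclusion rests on the supplied text alone, with 6112R and the consent forms unseen. The statistical analysis is unaffected. Because the collected sample is already being analysed, the change may reach few or no doses here. Its main value may lie in reuse of the schedule, since the pilot is meant to support a later randomised trial.

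**What to change.** For any further dosing under this protocol, or if the schedule is reused, add one line to VISIT 2 after consent and before randomisation: repeat the urine pregnancy test in the women tested at screening, and do not randomise or dose anyone who tests positive. Placing it before randomisation means that a positive result does not create a randomised participant without treatment.

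The cost is one urine test per woman, of a kind already in use, at an existing visit: about 0 to 2 tests among those now listed. There may be an occasional exclusion before randomisation. A very early pregnancy may still be missed, so the repeat test narrows the gap without closing it fully.
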